- b. A member of the research team will go in person to each clinic once per week to ensure that the pilot phase is running smoothly and optimally.
- c. A member of the research team will conduct telephone interviews with these families one week after enrollment. These phone calls will determine how the device is working, if participants foresee any obstacles to the use of the device, and to answer any other questions participants might have.
- d. A member of the research team will reach out to enrolled parents via phone, text, or email once a week (4 times in total) to inquire about how well the device is working, and if this is a feasible Platform to use.
- e. After 30 days, a member of the research team will again conduct interviews to get feedback. This pilot group will continue to use the device for one full year and will assist us with trouble shooting throughout the intervention.

4. Enrollment/Visit 1/Baseline Measurements

Informed online consent will be obtained at the time of enrollment. The consent form will be stored utilizing REDCap, which is a secure, online software. Families in the Intervention arm will receive Remote Health Management sensors. Data collected at the time of enrollment will include the following for each participant:

- c. Basic demographic and clinical history data (obtained by a review of medical records)
 - a. Include: name, date of birth, date of asthma diagnosis, zip code, history of a course of oral corticosteroid, current medications, phone call/email history to the clinic, asthma exacerbation history, and history of asthma-related ED visits and hospitalizations.
- d. Parent questionnaires, including the Asthma Control Test (ACT), Parental Asthma Management Self Efficacy (PAMSE) scale, and the Pediatric Asthma Caregiver's Quality of Life Questionnaire (PACQLQ).

All enrolled children, regardless of study arm, will have allergen testing via ImmunoCAP. This is a simple blood draw that can help further guide the knowledge and overall managements of child's asthma. This will be incorporated into the Remote Health Management software for the intervention group and be disclosed to the control group as well. The volume of the blood to be drawn for the assessment is 1.3 mL of serum or plasma is required to process the allergen panel we intend to use in the study.

5. Daily Inhaler Use Management

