The Remote Health Management team (Propeller Health) utilizes telehealth concepts, including an FDA-approved sensor, mobile apps, predictive analytics, and feedback to help patients and providers better manage asthma.^{11,12} The sensor monitors the use of inhaled medications (ICS and SABA), capturing the date, time, and number of uses. The sensor transmits this information via Bluetooth to a paired smartphone or hub. The location of the event is also securely uploaded to the cloud if the sensor is connected to the Smartphone at the time the sensor is used. Data can be uploaded to the caregiver's smartphone and to the patient's web portal, which their healthcare team will have access to help overall management.¹³

The sensors will be distributed to participants by the study team. We will aim for participants to engage with the study team before going to the clinic or hospital so the device is ready to use at the time of their appointment. This will require the participants to call the research team and the consent being described over the phone to the participants. At their appointment and when the device is given, the participants will sign the consent.

6. Randomization

After recruitment, participants will be stratified by age, sex, and insurance status. They will then be randomly assigned to one of the two study arms.

After recruitment, participants will be stratified by age (4-7 vs 8-17), sex (M vs F), and insurance type (private vs. public), resulting a total of eight strata (stratum1: 4-7, M, Private, stratum2: 4-7, M, Public, stratum3: 4-7, F, Private, etc.). Since this is not a double-blind study and no centralized randomization system will be implemented, one randomization schedule will be generated for each site. Each randomization schedule will contain all eight strata. To ensure balanced treatment allocations within each stratum, 20 randomization blocks will be generated within each stratum. Each block has a block size of 4 with a random permutation of treatments A and B (eg, block 1=AABB, block2=ABBA, etc). Each site's randomization schedule will begin with a distinct randomization sequence number which is different from the subject ID number. For example, site 1's randomization schedule will begin with randomization sequence number 100001, site 2's randomization schedule will begin with randomization sequence number 2000001, etc.

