| 9 month surveys | | | | | | | | | | | | | |
| Phone/email Follow-up | | | | | X | X | X | X | X | | | | |
| Epic Data Pull | | X | X | X | X | X | X | X | X | X | X | X | X |

| Tasks | Year 2 | | | | | | | | | | | | |
|------------------------------------|--------|-----|-----|-----|-----|-----|-----|-----|-----|-----|-----|-----|---|
| | Sept | Oct | Nov | Dec | Jan | Feb | Mar | Apr | May | Jun | Jul | Aug | |
| Retention Phase | | | | | | | | | | | | | |
| 9 month surveys | x | x | x | X | X | X | X | X | X | X | X | X | X |
| End of the Study Surveys | x | X | X | X | X | X | X | X | X | X | X | X | X |
| Remote Health Management Data Pull | X | X | X | X | X | X | X | X | X | X | X | X | X |
| Web Portal Data Pull | X | X | X | X | X | X | X | X | X | X | X | X | X |
| Feasibility Assessment | | X | X | X | X | X | X | | | | | | |
| Analysis Phase | | | | | | | | | | | | | |
| Data Analysis | | X | X | X | X | X | X | X | X | X | x | | |
| Publications and Presentations | | | | X | X | X | X | X | X | X | X | X | X |

Clinical Outcomes

| Source | Outcome | Time Point |
|--------------------------------------|--|------------------------|
| Remote Health Management Application | ICS and SABA use | Monthly download |
| Web Portal/Epic | Asthma-related ED visits, hospitalizations, and oral corticosteroid prescriptions/courses | Monthly Epic data pull |
| Web Portal/Epic | Patient demographics pulled | Baseline |
| Parent report (Survey) | Patient age, family income, race, family makeup (single parent, two-parent household, etc) | Baseline |

| | | |
|---|--|---|
| Asthma Control Test (ACT) (ages 12 and older Or Childhood Asthma Control Test (ages 4-11) | Parent report of their child's asthma control | 5 times in total (baseline, 3 months, 6 months, 9 months, study completion) |
| Parent-reported Values (un-validated) | Asthma-related oral corticosteroid prescription/use/courses; number of asthma-related hospitalizations; number of asthma-related ED visits | 5 times in total (baseline, 3 months, 6 months, 9 months, study completion) |
| ImmunoCAP Allergen Testing | Environmental Allergens | Baseline |

Psychosocial Outcomes

| Source | Outcome | Time Point |
|---|---|---|
| Parental Asthma Management Self-Efficacy (PAMSE) | Parental self-efficacy survey to assess parent's ability to manage and/or prevent acute exacerbations | 5 times in total (baseline, 3 months, 6 months, 9 months, study completion) |

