- Proventil HFA
- Ventolin HFA
- Xopenex

Supported Controller/Daily Medications:

- Advair HFA
- Advair Diskus
- Asmenex
- Combivent Respimat
- Dulera
- Flovent Diskus
- Flovent HFA
- QVAR
- Serevent Diskus
- Spiriva Respimat
- Striverdi Respimat

Timeline

Pilot: November 2016

- Pilot group of 8-10 families

Phase 1: Enrollment

- December 2016-December 2017
- Collect EMR data from the previous year
- Randomization

Phase 2: Intervention

- December 2016-December 2018
- Intervention Group will have the Remote Health Management device for 1 year
- Standardized Group will receive enhanced, standardized asthma education
- Each group will fill out the following surveys 5x during the study period:
 - ACT
 - PAMSE
 - PACQLQ
 - iTRACC Survey (Control Arm) or Intervention Survey (Intervention Arm)
 - Number of hospitalizations, ED visits, exacerbations
- We will pull information from the EMR to determine oral corticosteroid use

Phase 3: Analysis

- January 2018- December 31, 2018
- All data analyzed
- Preparation and submission of academic abstracts and papers

- Help to prepare for full scale rollout, if applicable
- Semi-structured interviews of subsample of participants
- Semi-structured interviews of health providers in the trial

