# **Statistical Analysis:**

### Demographic and baseline characteristics:

Demographic and baseline characteristics including gender, age, race, ethnicity, and co-morbidities will be summarized for each treatment group and overall. The demographic and baseline characteristics summary will be based on all randomized subjects.

Baseline values for efficacy parameters (ACT, quality of life score, PAMSE) will also be presented for each treatment group and overall based on all randomized subjects.

For continuous variables, non-missing will be used to calculate the mean, median, SD, IQR, minimum and maximum by treatment group and overall. For categorical variables, the count and percentages of each possible value will be tabulated by treatment group and overall.

All comparisons of baseline characteristics between treatment groups will be adjusted for potential household clustering using robust standard errors. For continuous variables, comparability of treatment groups will be assessed using general linear models. For discrete variables, comparability will be assessed using the Cochran-Mantel-Haenszel general association test. P-values will be displayed as descriptive statistics of comparability in order to identify potential baseline imbalances with an alpha level of 0.05.

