# AIM 1. Determine factors influencing clinical and psychosocial outcomes.

Clinical and psychological outcomes of interest include the 12-month rate of asthma-related oral corticosteroid use, ED visits, and hospitalizations, as well as change in mean ACT scores (range of 0 to 27) from baseline to end line (12 months). Psychological outcomes of interest include quality of life score (range of 1 to 7), parental self-efficacy score, and the number of school days missed due to asthma. Potential predictors of outcomes include age (4 to 7 years vs. 8 to 17 years), gender (M vs. F), race/ethnicity (non-Hispanic white, non-Hispanic Black, Hispanic, vs. others), insurance status (private/public), and co-morbidities.

Each count variable (asthma-related oral corticosteroid use, ED visits, and hospitalizations) will be analyzed by mixed negative binomial regression analysis adjusting for treatment, all potential predictors, and including maximal random effect structures (i.e., slope and intercept as allowed by the model) of family and clinic. VIFs (variance inflation factors) will be computed for each predictor. Highly correlated predictors (i.e. predictors that can be well-explained by other predictors) will be dropped from the model to avoid multicollinearity issues. Model fit criteria, parameter estimates, and precision of parameter estimates will all be evaluated to select the most parsimonious model.

For each continuous primary outcome variable (i.e., ACT score), change-from-baseline score at each visit will be analyzed using mixed linear regression models, adjusting for treatment, time point, baseline score, all potential predictors, and including random effects (i.e., both slope and intercept) of family and clinic. A treatment by time interaction will be included to evaluate whether the effect of the treatment on the primary outcome varies by time point. VIFs will be investigated for each predictor, and those with high VIFs (VIF>=10) will be dropped from the model to avoid multicollinearity issues. An unstructured covariance (UN) matrix will be assumed. Model fit criteria, parameter estimates, and precision of parameter estimates will also be used to select the most parsimonious model. Model diagnostics will be performed to check model assumptions. All analyses will be performed using statistical analytic software Stata Version 15.1.

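### The count models for three of the four primary outcomes name no prior-year event count as a covariate, which costs some precision but not validity

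*SAP*

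**What the plan says.** The protocol (Data Analysis, Primary Outcomes) names four primary outcomes: ACT, hospitalizations, ED visits and OCS use. The last three are counts over 12 months.

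- **Count models** (SAP, AIM 1; same wording in the protocol's AIM 1 analysis): negative binomial regression, "adjusting for treatment, all potential predictors, and including maximal random effect structures", for family and clinic. The list of potential predictors gives age group, gender, race/ethnicity, insurance and co-morbidities. Model criteria "will all be evaluated to select the most parsimonious model".
- **ACT model** (same section): change from baseline, "adjusting for treatment, time point, baseline score, all potential predictors". Baseline score is named in addition to the predictor list.
- **Randomization** (protocol, section 6): "participants will be stratified by age (4-7 vs 8-17), sex (M vs F), and insurance type (private vs. public"). Event history is not a stratification factor.
- **Baseline table** (SAP, Demographic and baseline characteristics): "Baseline values for efficacy parameters (ACT, quality of life score, PAMSE) will also be presented for each treatment group". Event counts are not among the values named.
- **Data on prior events**: the enrolment chart review (protocol, section 4) covers "asthma exacerbation history, and history of asthma-related ED visits and hospitalizations" as well as OCS history. The Clinical Outcomes table has parents report OCS courses and the "number of asthma-related hospitalizations; number of asthma-related ED visits", with baseline as one of the time points. Phase 1 of the Timeline adds "Collect EMR data from the previous year".

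**The concern.** A child's own recent event count is usually one of the better predictors of the next year's count. Here it is neither balanced by the stratification nor named in the models, and no text commits to showing it by arm. If the arms differed by chance in event history, the plan has no stated way to show this or allow for it on three of the four primary outcomes. Between-child variation that the prior count could explain would also stay in the error of the treatment estimate. The sponsor already intends to gather the history, so the omission gives up precision that could be had cheaply.

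**Working it through.** **Inputs from the documents.** Exacerbation rates 0.75 (control) and 0.545 (intervention), 20% drop-out, two-sided 0.05, 85% power and 250 children (protocol, Sample Size Determination). At least one OCS course in the past year is required for entry (protocol, section 2).

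**Reproducing the plan's figure.** (0.545/0.455)/(0.75/0.25) = 0.39927, log = -0.91812, as stated. A Wald test on the log odds ratio needs (1.960 + 1.036)² × [1/(0.545×0.455) + 1/(0.75×0.25)] / 0.91812² = 99.76 per arm. That is 199.5 in total, and 199.5/0.80 = 249.4, so 250. The calculation therefore treats both figures as proportions with an event. The planned analysis is of 12-month counts, so both readings are carried below.

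**Assumptions, because the documents give no dispersion, between-year correlation or yearly event rates.** Gamma frailty; dispersion k = 0.5 to 1; between-year correlation ρ = 0.5 to 1; exacerbations taken as OCS courses; 125 × 0.80 = 100 children per arm; prior count fully captured unless stated.

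**Hand check for events without an entry rule.** With yearly rate μ, the prior count explains a share ρ²kμ/(1+kμ) of between-child variation. That variation makes up 2k/(1/μ₀ + 1/μ₁ + 2k) of the variance of the log rate ratio. The fall in variance is roughly the product. At μ = 0.2 in both arms:
- k = 1, ρ = 1: (0.2/1.2) × (2/12) = 2.8%.
- k = 0.5, ρ = 0.5: 0.25 × (0.1/1.1) × (1/11) = 0.2%.

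**OCS needs simulation**, because entry truncates the prior count at one. Negative binomial models were fitted with and without the log prior count in large simulated samples. On the proportion reading, rates were solved so that 75% and 54.5% of children have an event. This gives 1.8-2.7 events a year in controls and a rate ratio of 0.42-0.51. Fall in variance with no other predictors:

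| Dispersion | ρ = 0.5 | ρ = 0.7 | ρ = 1 |
|---|---|---|---|
| 0.5 | 3.0% | 5.5% | 9.5% |
| 1 | 6.8% | 12.2% | 20.4% |

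Repeating this with fresh draws moved each figure by less than half a point. With five clinics and four binary predictors in both models, by the share of between-child variation that those predictors already explain:

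| Setting | 0% explained | 25% | 50% |
|---|---|---|---|
| OCS, proportion reading | 3.2-21.3% | 2.3-17.7% | 1.3-12.5% |
| OCS, 0.75 as on-study yearly rate | 0.8-4.9% | 0.5-4.4% | 0.3-2.6% |
| Event at 0.2/year (assumed) | 0.2-2.6% | 0.1-1.6% | 0.1-0.8% |
| Event at 0.5/year (assumed) | 0.7-9.6% | 0.6-6.1% | 0.3-3.4% |

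**In children.** On the proportion reading the gain is worth 200/(1-0.013) = 203 to 200/(1-0.213) = 254 children, that is 3 to 54 more on 200. On the yearly-rate reading the upper end is 200/(1-0.049) = 210.

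**In power.** On the proportion reading, OCS power at the planned effect exceeds 99% with or without the covariate. On the yearly-rate reading it rises by 0.2 to 1.4 points (35.8 to 36.0% at one end, 34.1 to 35.5% at the other).

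**Chance imbalance.** A 1-in-20 imbalance (1.96 SD) in mean log prior OCS count moves the OCS rate ratio by a factor of 1.05-1.14 with nothing explained by the listed predictors, and 1.03-1.08 with 50% explained (proportion reading).

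**Incomplete capture.** If 30% of prior events were missed (an assumption), the OCS variance falls without predictors drop from 2.9-20.4% to 1.8-13.5% (proportions) and from 0.9-4.6% to 0.3-1.7% (yearly rates).

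**Validity.** With 100 per arm and 2,000 replicates, null rejection was 4.7-5.9% without the covariate and 4.8-6.1% with it. Family clustering was not simulated.

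**The case against.** *The lists are open.* Both the predictor list and the baseline characteristics are introduced by forms of the word include, so event history is not excluded. That is right: the gap is one of specification. But an open covariate set for a primary outcome, followed by parsimony selection, leaves the term to be added or dropped after the data are seen.

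*The ACT contrast is weak.* ACT is analysed as a change score, where baseline adjustment also deals with regression to the mean. A reader might infer that the SAP contradicts itself. It does not, since different outcome types may take different covariates. The ACT model shows only that the plan names a baseline value separately when it wants one.

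*The prior count may be incomplete.* Follow-up contacts ask parents about events because out-of-network visits may not appear in the EMR (protocol, sections 8-12), and the same would hold for the prior year. The OCS history in section 4 carries no count or time window. The Timeline does not say which events the previous-year extract covers, and the parent-reported counts are labelled un-validated. All of this stands. It shrinks the gain but does not bias the comparison.

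*Aim 1 also reads predictor associations from this model.* Prior events may reflect the same factors, so adding them can weaken those associations and changes their meaning. This stands and shapes the fix.

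*A larger power gain is tempting.* A reader might pair the ratio 0.545/0.75 = 0.727 with the 1.8-2.7 events a year of the proportion reading and find gains of 1.7 to 12 points. That joins the effect from one reading to the control rate from the other. No section supports the pair, so it is at most a hypothetical smaller effect.

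**Conclusion.** The point holds as a matter of precision and pre-specification. No prior-year count is named in the models for three primary outcomes, and neither the stratification nor the baseline table makes up for it. A reader might infer that the treatment comparison is biased. It is not: randomization protects it, and the simulated error rate is near 5% with or without the term.

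The benefit is modest and uncertain. Under the stated frailty, dispersion and correlation assumptions, the OCS variance falls by roughly 1-21% on the proportion reading, with no practical change in power at the planned effect. On the yearly-rate reading it falls by roughly 0.3-5%, or about one point of power. For an event as rare as 0.2 a year the fall is 0.1-2.6%. Greater dispersion would raise these figures and incomplete capture would lower them. The change is worth making because it costs little and makes the result easier to defend should the arms differ in event history.

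**What to change.** In the treatment-effect model for each count outcome, pre-specify log(prior-year count of the same event + 0.5) as a fixed covariate, exempt from the VIF and parsimony selection. Define the count over the 12 months before enrolment. Build it from the pre-enrolment EMR data, supplemented by the baseline parent report where that was obtained before the arm was known. Add the three prior-year counts by arm to the baseline table.

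Because Aim 1 also reports predictor associations, present those from the model without the prior count as well.

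The cost is a short SAP addition, one covariate per model, three table rows, a second fit for the associations, and a written definition of what the previous-year EMR extract must contain. No extra patients or visits are needed. The SAP should acknowledge that out-of-network prior events may be missed.

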Clinical and psychological outcomes of interest include the 12-month rate of asthma-related oral corticosteroid use, ED visits, and hospitalizations, as well as change in mean ACT scores (range of 0 to 27) from baseline to end line (12 months). Psychological outcomes of interest include quality of life score (range of 1 to 7), parental self-efficacy score, and the number of school days missed due to asthma. Potential predictors of outcomes include age (4 to 7 years vs. 8 to 17 years), gender (M vs. F), race/ethnicity (non-Hispanic white, non-Hispanic Black, Hispanic, vs. others), insurance status (private/public), and co-morbidities.

Each count variable (asthma-related oral corticosteroid use, ED visits, and hospitalizations) will be analyzed by mixed negative binomial regression analysis adjusting for treatment, all potential predictors, and including maximal random effect structures (i.e., slope and intercept as allowed by the model) of family and clinic. VIFs (variance inflation factors) will be computed for each predictor. Highly correlated predictors (i.e. predictors that can be well-explained by other predictors) will be dropped from the model to avoid multicollinearity issues. Model fit criteria, parameter estimates, and precision of parameter estimates will all be evaluated to select the most parsimonious model.

For each continuous primary outcome variable (i.e., ACT score), change-from-baseline score at each visit will be analyzed using mixed linear regression models, adjusting for treatment, time point, baseline score, all potential predictors, and including random effects (i.e., both slope and intercept) of family and clinic. A treatment by time interaction will be included to evaluate whether the effect of the treatment on the primary outcome varies by time point. VIFs will be investigated for each predictor, and those with high VIFs ($VIF \geq 10$) will be dropped from the model to avoid multicollinearity issues. An unstructured covariance (UN) matrix will be assumed. Model fit criteria, parameter estimates, and precision of parameter estimates will also be used to select the most parsimonious model.

Model diagnostics will be performed to check model assumptions. All analyses will be performed using statistical analytic software Stata Version 15.1.

AIM 2. Enhance parental management through improved inhaler use.

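### The final model for each primary outcome is chosen after the data are seen, with no term protected, so control of the 5% error for the treatment effect is not assured

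*SAP*

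**What the plan says.** The protocol (Data Analysis, Primary Outcomes) lists four primary outcomes: ACT, asthma hospitalisations, asthma ED visits and oral corticosteroid use. The SAP section on Aim 1 gives their models, and the protocol's Statistical Analysis section repeats them.

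- **Starting model, counts:** mixed negative binomial regression, "adjusting for treatment, all potential predictors, and including maximal random effect structures (i.e., slope and intercept as allowed by the model) of family and clinic".
- **Starting model, ACT:** mixed linear regression of change from baseline, "adjusting for treatment, time point, baseline score, all potential predictors, and including random effects (i.e., both slope and intercept) of family and clinic". In addition, "A treatment by time interaction will be included to evaluate whether the effect of the treatment on the primary outcome varies by time point".
- **Candidate predictors:** "Potential predictors of outcomes include age (4 to 7 years vs. 8 to 17 years), gender (M vs. F), race/ethnicity", followed by insurance and co-morbidities.
- **Collinearity step:** for counts, "Highly correlated predictors (i.e. predictors that can be well-explained by other predictors) will be dropped from the model to avoid multicollinearity issues", with no cut-off. For ACT, "those with high VIFs (VIF>=10) will be dropped from the model to avoid multicollinearity issues".
- **Final step:** for counts, "Model fit criteria, parameter estimates, and precision of parameter estimates will all be evaluated to select the most parsimonious model". For ACT, "Model fit criteria, parameter estimates, and precision of parameter estimates will also be used to select the most parsimonious model".

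Neither document names the fit criterion, a threshold, an order of removal or the terms that may be removed. Neither says that the selection is blind to treatment. The SAP's sensitivity analyses are multiple imputation and whatever else is judged appropriate; the full starting model is not kept as one of them.

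**The concern.** One regression does two jobs: it estimates the randomised treatment effect and it searches for factors that influence outcome. Reducing a model on the data can be acceptable for the second job if it is labelled exploratory. For the first, a p-value or interval computed as if the final model had been fixed beforehand takes no account of the choosing.

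The treatment coefficient and its standard error are among the estimates and precisions that the rule consults. Three kinds of term are exposed: the factors used to stratify randomisation (age group, sex, insurance; Protocol, section 6), the baseline ACT score, and the family and clinic random effects, which determine the standard error. The published result would not show which version of the rule had been applied. For Aim 1 itself, a factor reported because it looked strong enough to keep will tend to look stronger than it is.

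**Working it through.** **1. The plan's error rate and evaluable number.** The Aim 1 models state no alpha. The two-sided 0.05 comes from the protocol's Sample Size Determination, whose figure reproduces:

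n per arm = (z0.975 + z0.85)² × [1/(p1(1−p1)) + 1/(p2(1−p2))] / log(OR)²
= (1.960 + 1.036)² × [1/(0.545×0.455) + 1/(0.75×0.25)] / 0.9181²
= 99.76, rounded up to 100.

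With 20% drop-out, 100/0.8 = 125 per arm, or 250 in total. The evaluable number used below is 250 × 0.8 = 200. Every other data-generating value below is an assumption.

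**2. Selecting baseline covariates, linear outcome.** Inputs: no treatment effect, 100 per arm, six binary covariates with equal effects, all 2⁶ = 64 subsets fitted, 10,000 to 20,000 runs (Monte Carlo SE about 0.002). Two-sided rejection rate for treatment:

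| Covariate effect (SD) | Full model fixed | Best AIC | Best BIC | Smallest treatment SE | Smallest treatment p |
|---|---|---|---|---|---|
| 0.1 | 0.048 | 0.052 | 0.052 | 0.053 | 0.070 |
| 0.2 | 0.052 | 0.056 | 0.054 | 0.057 | 0.089 |
| 0.4 | 0.048 | 0.050 | 0.055 | 0.054 | 0.126 |

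**3. Selecting baseline covariates, counts.** Inputs: negative binomial, mean 0.75, dispersion 1, 200 children, five predictors (2⁵ = 32 subsets), 1,500 null trials. Rejection was 5.6% with the full model fixed, 6.1% with the AIC-best model and 11.1% with the smallest treatment p. The Monte Carlo SE is √(0.05×0.95/1500) = 0.6 points, so 5.6% and 6.1% cannot be told apart from each other or from 5%.

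**4. Selecting a clinic random slope.** The protocol plans at least four of five listed sites. The documents do not say which slope is meant; a treatment slope by clinic is assumed here. With C equal clinics sharing 200 children and unit outcome SD, each clinic's effect estimate has sampling variance v = 4/(200/C). True clinic effects vary with SD τ around zero. The model with the slope is a t-test on C−1 df; without it, a z-test with variance v/C. The slope is dropped when Cochran's Q is non-significant at 5%. There were 200,000 runs.

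| C | τ | Always kept | Dropped if non-significant | Kept or dropped by which gives significance |
|---|---|---|---|---|
| 4 | 0 | 0.050 | 0.047 | 0.082 |
| 4 | 0.1 | 0.049 | 0.059 | 0.093 |
| 4 | 0.2 | 0.050 | 0.093 | 0.132 |
| 4 | 0.3 | 0.050 | 0.125 | 0.193 |
| 5 | 0 | 0.050 | 0.048 | 0.080 |
| 5 | 0.1 | 0.050 | 0.057 | 0.088 |
| 5 | 0.2 | 0.050 | 0.085 | 0.118 |
| 5 | 0.3 | 0.049 | 0.111 | 0.169 |

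Hand check of the mechanism at C = 4, τ = 0.3: v = 0.08. The mean has true variance (0.09 + 0.08)/4 = 0.0425, but the reduced model assumes 0.02. The effective cut-off is 1.96/√(0.0425/0.02) = 1.34, giving about 0.18 if the slope is always dropped; the simulation gave 0.179. The Q test failed to keep the slope in 70% of those runs.

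**5. Exaggeration of Aim 1 factors.** Assume a true rate ratio of 1.30, 40% prevalence (80 against 120 children), and mean and dispersion as in step 3. Then SE = √[((1 + 0.75)/0.75) × (1/80 + 1/120)] = 0.220, and the true z is log(1.30)/0.220 = 1.19. AIC keeps a one-parameter factor when |z| > √2 = 1.414. The probability of keeping it is 0.416. Its average log rate ratio when kept is 1.76 times the truth: exp(1.76 × 0.262) is about 1.59.

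**The case against.** The strongest reply is that the starting models are pre-specified and that ordinary parsimony does little harm. That stands for baseline covariates: in steps 2 and 3, AIC and BIC leave error within about a point of 5%, and losing a stratification factor mainly costs precision. It does not cover the random effects in step 4, where a conventional drop-if-non-significant rule gave up to 12.5% under the assumed slopes.

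A reader might infer several stronger things that the documents do not support:

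- **That the reported p-values will be wrong, or that the error is 11% or more.** The smallest-p columns are worst cases. The text permits the treatment estimate to guide the choice but does not prescribe it, and it aims at parsimony, not at the most favourable effect. The protocol says the trial is not double-blind; that does not show that models are selected with the treatment result in view.
- **That null factors will be declared significant 32% of the time instead of 5%.** Given that a null factor is kept by AIC, the chance of p<0.05 is 0.05/0.157 = 32%. That is a conditional rate. The unconditional rate in the same calculation is still 5%.
- **That the VIF step biases the treatment effect.** VIF uses covariates only. A VIF of 10 needs R² of 0.9, unlikely for age group, sex or insurance. The missing cut-off for counts is untidy, and different covariate sets for different outcomes are not in themselves an error.

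It can also be said that treatment and baseline score are named apart from the potential predictors. That separation bears on the VIF steps; the parsimony sentences make no such exception.

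**Conclusion.** The point holds as a lack of assurance. The plan states a data-driven rule for the final model of every primary outcome, and that model also carries the treatment comparison. Its actual error could lie anywhere from essentially nominal to well above it:

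- about 5-6% if only baseline covariates are selected by AIC or BIC;
- about 7-13% in the worst case where the treatment estimate guides the covariate choice;
- 4.7-12.5% if a clinic treatment slope is dropped when non-significant, and 8.0-19.3% if it is kept or dropped by which version gives significance.

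Models fixed in advance stayed at 4.8-5.2% in the linear and clinic simulations. The inflation of retained Aim 1 factors occurs even under plain AIC selection and does not depend on anyone looking at the treatment effect.

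The simulations are simplified (no family effects, linear or two-stage for the most part) and rest on assumed covariate effects, dispersion and clinic variation. They show direction and range; they do not predict this trial's error rate. The sample size of 250 is not affected.

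**What to change.** For the treatment effect on each primary outcome, replace the parsimony sentence in the SAP and the protocol with one model fixed in advance:

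- treatment;
- the randomisation factors: age group, sex and insurance;
- the baseline value, and for ACT also time point and treatment by time;
- the planned family and clinic effects in a stated structure that says which slopes are meant, simplified only for non-convergence and in a stated order.

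State that no fixed-effect term is removed on the basis of outcome data, and state the alpha for these models in the SAP. The listed count models contain no baseline count, so the SAP should define one; the protocol's Timeline already plans to collect the previous year's EMR data.

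Move the VIF and parsimony steps to a separate Aim 1 factor model labelled exploratory, and report its full form beside any reduced form.

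The cost is a few sentences and a few degrees of freedom that selection might have saved. Keeping a clinic treatment slope with four or five clinics leaves few degrees of freedom for the treatment test, so whether it belongs in the structure should also be decided before the outcome data are seen.
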